### **4.6. Handling of Missing Data for Efficacy and Safety Endpoints**

#### **4.6.1. Imputation for Missing Baseline Values**

Subjects are expected to have baseline values for safety and efficacy assessments in Study ATB200-07 and so no rule for baseline imputation is needed, unless otherwise specified.

#### **4.6.2. Imputation for Missing Post-baseline Values**

Missing post-baseline values (whether efficacy or safety) will not be imputed.

### **4.7. Missing AE Attributes**

Adverse events with missing attributes will be imputed with the worst possible outcome, for summary purposes. For example, if an adverse event (AE) is missing relationship to study drug, it will be imputed as being ‘related’ to the study drug; if an AE is missing the severity level, it will be imputed as being ‘severe.’

Nonetheless, in the data listings, the actual observed values will be reported. That is, if the response is missing, it will show as missing in the data listings.

#### **4.7.1. Missing or Partial AE Onset or Medication Start Date**

Complete dates are very important to correctly describe safety events such as TEAEs and designation of unique AE occurrences. When dates are completely missing or partially missing, they will be imputed.

The following algorithm will be used to impute partial or missing AE start dates:

1. If year is not missing and is after the year of first application of study drug:
  - If month is missing, then month will be imputed as January.
  - If day is missing, then day will be imputed as the first of the month.
2. If year is not missing and is the same as the year of the first application of study drug:
  - If month is missing, then impute the month as the month of the first application of study drug.
  - If day is missing but month is the same as the month of first application of study drug, then impute day as the first day of study drug application.
  - If day is missing but month is after the month of first application of study drug, then impute day as the first of the month.
3. If year is missing, then impute the year as the year of the first application of study drug:
  - If month is missing, then impute the month as the month of the first application of study drug.
  - If day is missing, then impute the day as the day of the first application of study drug.
4. If the start date is completely missing, but the AE is either ongoing or the stop date is after the first date of drug application, then impute the start date as the first application of study drug.
5. If using the above rules, the stop date is before the start date, then leave the start date missing and assume that the AE is treatment-emergent for the purpose of the analysis.

No imputations will be applied to AE stop dates.

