#### **12.3.7. Adverse Events**

Reporting of AEs begins after the first dose of open-label study drug in this study. As required by their institutions, investigators will be responsible for reporting AE information to their IRB, IEC, or REB (see Section 13). If the start date of an AE is before the first dose of open-label study drug, it should be captured as medical history.

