### 7.2. Analysis of Adverse Events

Adverse events will be coded by system organ class (SOC) and preferred term (PT) using MedDRA version 23.0.

Summaries of AEs and SAEs will be focused on treatment-emergent adverse events (TEAEs) pertaining to Study ATB200-07 only. These are defined as any event that started or changed in the severity on or after the first dose of study drug in Study ATB200-07.

As stated in Section 5.2.3, AEs from ATB200-03 will be part of the medical history for ATB200-07. However, if those AEs worsened (or increased in severity) on/after first dose in ATB200-07, they will be considered as TEAEs for ATB200-07. For AEs occurring on Day 1 of ATB200-07, if the start time of the event is missing or if it occurred after the administration of the first dose of study drug, the event will be considered a TEAE.

In general, adverse events that occur more than 30 days from the last dose of study drug will not be counted as treatment-emergent. Therefore, if a subject permanently discontinues study drug and then gets an AE, the event will be considered as a TEAE only if it is within the TEAE tabulation period (in days) calculated as  $[(\text{last dose date of study drug} + 30 \text{ days}) - \text{first dose date} + 1]$  from the last dose date.

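### For ordinary partial AE start dates, SAP 4.7.1 rule 5 labels as treatment-emergent an event recorded as over before the first dose, against the SAP's own definition

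*SAP*

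**What the plan says.** SAP 4.7.1 gives five ordered rules for incomplete AE start dates.

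- Rule 1 applies "If year is not missing and is after the year of first application of study drug". It fills in January, or the first of the month.
- Rule 2 covers a start in the first-dose year. A missing month becomes the first-dose month. If the month is the first-dose month, the instruction is to "impute day as the first day of study drug application". In a later month the day becomes the first.
- Rule 3: "If year is missing, then impute the year as the year of the first application of study drug". Missing month and day are likewise copied from the first dose.
- Rule 4 uses the first-dose date under this condition: "If the start date is completely missing, but the AE is either ongoing or the stop date is after the first date of drug application".
- Rule 5 deals with a conflict left by the others: if "the stop date is before the start date, then leave the start date missing and assume that the AE is treatment-emergent".

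The section closes with "No imputations will be applied to AE stop dates". The stop date that triggers rule 5 is therefore a recorded one.

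On treatment-emergent events, SAP 7.2 states: "These are defined as any event that started or changed in the severity on or after the first dose of study drug". Protocol 13.1.1 likewise requires onset after the first open-label dose. Protocol 12.3.7 adds: "If the start date of an AE is before the first dose of open-label study drug, it should be captured as medical history".

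**The concern.** An imputation rule for onset dates normally errs towards counting an event when its timing is unknown. Rule 5 looks like that kind of caution. In the commonest patterns of missing dates, however, the timing is known. The conflict that triggers the rule is a recorded end before the first dose, and that is the evidence that rules out treatment-emergence.

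TEAE incidence serves the primary objective, long-term safety and tolerability. A programmer who follows rule 5 literally would put an event that ended before ATB200-07 treatment into the TEAE tables, where the SAP's own definition says it does not belong.

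**Working it through.** **Logic.** Let D be the first-dose date, E the recorded stop date and S the imputed start. Rule 5 fires when E < S. Assume the recorded parts are correct, so the true onset is no later than E.

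| Missing part of start date | Known part | S | Rule 5 fires when |
|---|---|---|---|
| Day | Later month or year than D | First of that month, so S ≤ onset ≤ E | Never |
| Day | Same month and year as D | D | E < D |
| Day and month | Later year than D | 1 January, so S ≤ onset ≤ E | Never |
| Day and month | Same year as D | D | E < D |
| All | None | D, by rule 3 | E < D |

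In these patterns a firing implies E < D. An event that ended before D can neither start nor change severity on or after D, so it fails SAP 7.2.

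The last row depends on applying rule 3 to a fully missing date. Rule 4 is silent when the stop is before the first dose. If rule 4 alone is taken to govern fully missing dates, such an event gets no imputed start and no stated class.

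**Example (assumed dates).** First dose 10 March 2020; AE start recorded only as 2020; stop 15 February 2020. Rule 2 gives S = 10 March 2020. The stop is earlier, so rule 5 makes the event a TEAE, although it ended 14 + 10 = 24 days before the first dose (February 2020 has 29 days).

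**Check on synthetic dates.** The five rules were applied literally to events with true onset from 450 days before to 800 days after first dose, ten durations from 0 to 365 days, and three assumed first-dose dates. Each cell shows firings with stop before first dose / all firings.

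| Pattern | 10 Mar 2020 | 20 Jul 2020 | 5 Dec 2019 |
|---|---|---|---|
| Day missing | 25/25 | 70/70 | 8/8 |
| Day and month missing | 368/368 | 1,373/1,373 | 2,567/2,567 |
| All missing | 3,660/3,660 | 3,660/3,660 | 3,660/3,660 |
| Only month missing | 326/331 | 1,284/1,305 | 2,555/2,641 |
| Year and day missing, month known | 3,326/3,863 | 2,752/3,241 | 1,116/1,116 |
| Only year missing | 3,233/3,751 | 2,287/2,490 | 1,008/1,008 |

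The first three rows confirm the logic. The last three show its limit. With first dose 10 March 2020, rule 5 fired on a stop on or after first dose in 331 − 326 = 5, 3,863 − 3,326 = 537 and 3,751 − 3,233 = 518 cases. The counts depend on the assumed dates and durations. They test the logic and do not estimate any frequency in the trial.

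**Counter-example (assumed dates).** First dose 15 June 2020; start recorded only as December; true event 3 to 10 December 2020. Rule 3 gives S = 15 December 2020. The stop of 10 December is earlier, rule 5 fires, and calling the event treatment-emergent is right.

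**Size.** SAP 7.2.1.2 counts a subject once within an SOC and once within a PT. One misclassified event therefore adds at most one subject to a row: 1/110 = 0.9 percentage points of the planned overall number. It adds nothing if that subject already has a genuine TEAE in the row. Within one treatment group the denominator is smaller and the step larger; the documents do not give group sizes.

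**The case against.** **Such records should hardly exist.** This largely stands. Protocol 12.3.7 and 13.2 start AE recording after the first open-label dose, and SAP 5.2.3 makes ATB200-03 AEs part of medical history. Protocol Table 4 does mark AE collection at the Baseline Visit, but its footnote a limits that visit to subjects who did not complete Week 52 of ATB200-03. A pre-dose stop in the AE data may therefore be a misfiled event or a wrong stop date. That supports querying the record; it does not support a default that contradicts the definition.

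**SAP 4.7 adopts the worst case for missing attributes.** That suits real uncertainty, such as a Day 1 event with no start time (SAP 7.2). It does not fit a case where the recorded stop settles the order of events.

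**Other safeguards.** Data cleaning under protocol 14 may catch the inconsistency, and the listings keep observed values. Neither changes the class that the rule assigns in the tables. Protocol 15.3.3.3 wants date imputation similar to ATB200-03 for consistency. Whether rule 5 came from there cannot be checked, and consistency would not remove the conflict. SAP 1 says that the SAP supersedes the protocol on analysis, but the conflict with SAP 7.2 lies within the SAP.

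**Stronger readings.** A reader might infer that rule 5 is wrong whenever it fires; the December example refutes this. A reader might also infer that it captures every event that ended before first dose. It does not: a complete start date needs no imputation, and for a partial start in an earlier year, or in an earlier month of the first-dose year with the day missing, rules 1 to 3 have no branch.

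**Conclusion.** The defect is real but minor. With the day, the day and month, or the whole start date missing, rule 5 as written assigns treatment-emergence only to events recorded as ending before first dose, which SAP 7.2 excludes. This assumes that the recorded stop date is correct and, for fully missing dates, that rule 3 applies. With the year missing and the month known, or with only the month missing, rule 5 can also fire on a stop on or after first dose; there its assumption is a defensible worst case.

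The number of affected events cannot be computed, because the documents contain no AE data. It is probably very small. The 0.9 points is a ceiling per event and overall table row, based on planned rather than actual enrolment.

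**What to change.** Replace rule 5 with a rule that tests the stop date directly:

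*If the imputed start date is later than the recorded stop date, leave the start date missing. If the recorded stop date precedes the first ATB200-07 dose, query the record and, if the date is confirmed, treat the event as medical history and not as treatment-emergent. If the recorded stop date is on or after the first dose, assume the event is treatment-emergent.*

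No exception for later worsening is needed in the pre-dose branch, since an event that has ended cannot worsen afterwards. The cost is a short SAP edit and one extra condition in the TEAE derivation, with no new data collection.

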#### **4.7.2. Missing or Partial Medication Stop Date**

References to year and month are the year and month of the stop date:

1. If year and month are known and study medication stopped during that month and year, use the stop date of study medication.
2. If year and month are known and informed consent was provided during that month and year, use the date of informed consent.
3. If year and month are known and study medication stopped after the date of informed consent and not in the month that medication stopped, use the last day of the month.
4. If year and month are known and are prior to the month of informed consent, use the first day of the month.

5. If only year is known and study medication stopped during that year, use the stop date of study medication.
6. If only year is known and study medication stopped after that year, use December 31st of that year.
7. If only year is known and study medication stopped prior to that year, use the first day of the year.
8. Should any of the previous stop dates be created before a start date, either a complete date or an imputed one, use the (imputed) start date instead of the date that would otherwise be created.
9. Otherwise, if stop date is unknown, leave as missing.

## 5. CHARACTERISTICS OF STUDY POPULATION

Unless otherwise stated, the discussion of characteristics of study population will pertain solely to Study ATB200-07.

### 5.1. Subject Disposition

Disposition will focus on Study ATB200-07 only, and it will be presented by the treatment groups described in Section 4.2 and overall. The presentation will include the number of subjects who enrolled in the OLE study (OLE-ES), the number and percentage of subjects in the FAS, and the OLE safety population, number and percent of subjects who completed the study (based on the ‘Yes’ check box on the eCRF), and who discontinued the study early. The categories classifying the subjects’ study completion status are derived from the end of study electronic case report form (eCRF) page. The number and percent of subjects by reason of discontinuation will also be presented. As much as possible, any discontinuation with reason due to ‘other’ will be queried and re-categorized appropriately, by medical review.

### 5.2. Demographic and Baseline Characteristics for ATB200-07

Demographic and baseline characteristics will be summarized for the OLE enrolled subjects (OLE-ES) population with the descriptive statistics: n, mean, standard deviation (SD), median, first quartile (Q1), third quartile (Q3), minimum, and maximum (for continuous variables) and counts (number of observations) and percentage (for categorical variables), and presented by treatment group and overall.

#### 5.2.1. Demographics

- Categorical: Sex; race; region; and prior ERT status (ERT-experienced or previously ERT-naïve) as at the baseline in Study ATB200-03. The regions are pooled as follows: North/South America, Europe, Asian Pacific
- Continuous: Age at informed consent in ATB200-07; weight; height; and body mass index (BMI)

In addition, age at informed consent will be summarized as a categorical variable with the categories:

≥ 18 to < 35 years, ≥ 35 to < 50 years, ≥ 50 to < 65 years, ≥ 65 years

#### 5.2.2. Baseline Characteristics

- Continuous: 6MWD; FVC (sitting % predicted); CK; Hex4; age at first dose of prior ERT treatment (years) before entering Study ATB200-03 (for subjects who are ERT-experienced as defined in Section 4.3.1); and the duration of the prior ERT treatment (for subjects who are ERT-experienced as defined in Section 4.3.1)
- Categorical:
  - Age at first dose of prior ERT treatment (years) categorized:  
< 18 years, ≥ 18 to < 35 years, ≥ 35 to < 50 years, ≥ 50 years
  - Subjects with history of falls (Y, N) at the baseline in Study ATB200-07;

- Subjects with history of IARs (Y, N) at the baseline in Study ATB200-07;
- Prior pre-infusion medications versus no prior pre-infusion medications at the baseline in Study ATB200-07.

For partial dates involving age at diagnosis and age at first dose of prior ERT treatment, missing day will be imputed as ‘01,’ and missing month will be imputed as ‘JANUARY.’

The demographic and baseline characteristics summary will also be presented by the prior ERT status (ERT-experienced versus previously ERT-naïve).

### **5.2.3. Medical History**

The AEs from Study ATB200-03 together with medical history collected for Study ATB200-07 will constitute the complete medical history for the OLE Study ATB200-07. Medical history will be coded using version 23.0 of the Medical Dictionary for Regulatory Activities (MedDRA) into system organ class (SOC) and preferred term (PT). The frequency of subjects with medical history will be summarized on the OLE safety population by SOC and PT and presented by treatment group and overall.

### **5.2.4. Prior and Concomitant Medications and Nondrug Therapies**

Prior medications/nondrug therapies are defined as any medication or nondrug therapy that a subject receives prior to the start of the study drug. Concomitant medications/nondrug therapies are defined as those that (a) a subject receives prior to first dose of study drug and continues after the first dose of study drug, or (b) those medications and nondrug therapies that are initiated after the first dose of study drug. Medications/nondrug therapies that are initiated after the last dose of study drug will not be considered as concomitant medications.

Prior and concomitant medications will be coded using the World Health Organization Drug Dictionary (Global B3, March 2020). The number and percentage of subjects receiving prior medication, and number and percentage of subjects receiving concomitant medication will be summarized by anatomical therapeutic chemical (ATC) class of level 4 and preferred drug name for the OLE safety population and presented by treatment group. The summary results will be presented in order of decreasing frequency of the most common medication administered to the overall treatment group.

In addition to the summary of prior and concomitant medications, the pre-infusion medications will also be summarized. Both prior pre-infusion medication (ie, pre-infusion medications taken before the first dose of cipaglucosidase alfa IV infusion study drug) and pre-infusion medications during the study (ie, those that start on or after the first dose of study drug but before the last dose of study drug) will be summarized by treatment group and overall, for the OLE safety population.

A listing of all pre-infusion medications will be provided, and this display will include columns for subject ID, prior ERT status, ATC Level 4/drug name/report name, start date and time relative to Day 1, end date and time relative to Day 1, dose (unit)/route/frequency, ‘taken before start date?’, and ‘taken during start date?.’

Separate listings will be provided for all prior and concomitant medications, and all prior and concomitant nondrug therapies.

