### **12.3.3. Prior/Current Medications**

For subjects who participated in Study ATB200-03, any concomitant medications reported during Study ATB200-03 that have not been stopped before the Baseline Visit for this study will be recorded as prior medications.

All subjects will be asked to report any medications (including, to the extent possible, dosage, frequency, start dates, and stop dates) that they are currently taking. All prescription and nonprescription medications will be recorded. In addition, any nondrug therapies (including physiotherapy and occupational therapy) that a subject is undergoing are to be recorded. Details regarding use of ambulatory aids such as a cane or walker as well as respiratory support such as continuous positive airway pressure or bi-level positive airway pressure should also be recorded.

Medications/procedures will be reviewed at each study visit in order to capture any changes that occurred during the study period.

Concomitant medications and nondrug therapies (eg, procedures, surgery, physical therapy, or assistive devices) specifically associated with an AE or IAR should be entered into the corresponding eCRFs.

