In the event that a subject experiences an IAR, the subject should be premedicated for subsequent infusions with antihistamines, steroids, and/or acetaminophen, infusion rate adjustments, or other steps taken. If these measures are not successful, the investigator/designee should contact the medical monitor for guidance. The premedications should be continued for all remaining infusions.

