### **3. STUDY DESIGN**

#### **3.1. Summary of Study Design**

This is a multicenter, international, OLE study of ATB200/AT2221 (heretofore referred to as cipaglucosidase alfa/miglustat) in adult subjects with late-onset Pompe disease (LOPD) who completed the randomized double-blind Study ATB200-03. Study ATB200-07 consists of a treatment period that lasts until 31 December 2024 or until study termination by the sponsor, and it includes a 30-day safety follow-up period for the end of study (EOS) or early termination (ET) assessments.

All subjects in Study ATB200-07 are to be treated with cipaglucosidase alfa/miglustat every 2 weeks. Subjects who previously received alglucosidase alfa/placebo in Study ATB200-03 were switched to cipaglucosidase alfa/miglustat in Study ATB200-07, and subjects who received cipaglucosidase alfa/miglustat in Study ATB200-03 continued on cipaglucosidase alfa/miglustat in Study ATB200-07. The first infusion visit in this study was to be scheduled approximately 2 weeks after the last visit in Study ATB200-03 in an effort to ensure continued administration of study drug on the same schedule with no gap between studies. The end of study assessment in Study ATB200-03 will be considered the baseline assessment in Study ATB200-07, as described in Section 4.4.2.

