## 4.4. Data Handling

### 4.4.1. Study Day

For the purposes of analysis, the date of first dose of study drug (First Dose Date) in ATB200-07 is designated as Day 1 and it will serve as the reference start date. The following relative days are considered:

- Total duration of treatment (ie, exposure) will be calculated as: (last dose date prior to data cutoff – first dose date) + 1.
- If the date of interest occurs on or after the first dose date, then study day will be calculated as: (date of interest – first dose date) + 1.
- If the date of interest occurs prior to the first dose date, then study day will be calculated as: (date of interest – first dose date).

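### SAP 5.2.4 defines on-study pre-infusion medication by start date alone, so a premedication course carried over into ATB200-07 may be summarised as prior only

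*SAP*

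**What the plan says.** SAP 5.2.4 contains two classification rules.

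- **General medications.** The concomitant definition has two limbs. Limb (a) covers a drug that "a subject receives prior to first dose of study drug and continues after the first dose of study drug". Limb (b) covers a drug initiated after the first dose. Drugs begun after the last dose are not concomitant.
- **Pre-infusion medications.** The prior group is "pre-infusion medications taken before the first dose of cipaglucosidase alfa IV infusion study drug". The during-the-study group is "those that start on or after the first dose of study drug but before the last dose of study drug". Both are to be summarised by treatment group and overall on the OLE safety population.

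SAP 4.4.1 fixes the reference date: "the date of first dose of study drug (First Dose Date) in ATB200-07 is designated as Day 1".

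Protocol 12.3.3 says how medication still running from the parent study enters this study: ATB200-03 concomitant medications "that have not been stopped before the Baseline Visit for this study will be recorded as prior medications". Protocol 13.1.3 says of a subject premedicated after an IAR: "The premedications should be continued for all remaining infusions". SAP 3.1 describes the transition as "continued administration of study drug on the same schedule with no gap between studies".

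SAP 5.2.4 also plans a listing: "A listing of all pre-infusion medications will be provided". Its columns include start and end date and time relative to Day 1, and frequency.

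**The concern.** The pre-infusion rule looks only at when a medication started. It does not ask whether the medication was still being given. A premedication begun before Day 1 and taken before every ATB200-07 infusion fails that test and is left in the prior row. Limb (a), in the same section, treats the same record as concomitant. The SAP gives no reason for the difference.

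Carry-over is plausible. The extension follows ATB200-03 without a planned gap. Protocol 6.1 says antihistamine and steroid premedication is in regular use with alglucosidase alfa, and one of the two reporting groups in SAP 4.2 came directly from that drug. SAP 5.2.2 makes prior pre-infusion medication, yes or no, a baseline characteristic, so the sponsor expects some subjects to have it.

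What is at stake is interpretation. Long-term safety and tolerability is the primary objective, IAR frequency and severity is a safety endpoint, and SAP 7.2.2.5 examines whether IARs fade over time or emerge late. A reader of those tables will want to know how many subjects were infused under premedication. The row that appears to answer this may omit subjects who were.

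**Working it through.** The plan gives no figure to reproduce, so the check applies each rule as written to test records.

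Rules, using whole days as in SAP 4.4.1, with Day 1 the first ATB200-07 dose and L the last dose day:

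- Prior pre-infusion: start < 1.
- On-study pre-infusion, as written: start ≥ 1 and start < L.
- General concomitant: (start < 1 and stop ≥ 1) or (start ≥ 1 and start ≤ L). Limb (b) is taken to include Day 1.
- Overlap rule, for comparison: start ≤ L and stop missing or ≥ 1.

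The days below are arbitrary test values, with L = 1600.

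| Record | Prior | On-study, as written | Concomitant | On-study, by overlap |
|---|---|---|---|---|
| Start Day −200, ongoing | yes | **no** | yes | yes |
| Start Day −200, stop Day 300 | yes | **no** | yes | yes |
| Start Day −200, stop Day −10 | yes | no | no | no |
| Start Day 1, ongoing | no | yes | yes | yes |
| Start Day 50, ongoing | no | yes | yes | yes |
| Start and stop on Day 1600 | no | **no** | yes | yes |
| Start Day 1601 | no | no | no | no |

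Three things follow.

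1. In the first two rows the drug is used during ATB200-07, but the pre-infusion rule does not count it as on-study. The concomitant rule does count it.
2. Rows one and three give the same pair of pre-infusion answers (prior yes, on-study no), although one drug is still being given and the other stopped before Day 1. Neither pre-infusion summary, nor the two together, can therefore give the number of subjects premedicated during ATB200-07.
3. A medication that starts on the last dose day is also excluded when dates are compared, because the rule says before the last dose. This is a small edge case.

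The prior definition also needs its reference dose stated. It refers to the first cipaglucosidase alfa infusion, and continuing subjects had theirs in ATB200-03. SAP 4.4.1 makes the ATB200-07 reading the natural one. On the other reading, a course begun during ATB200-03 in a continuing subject would fall in neither group.

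**Size, as illustration only.** Let N be the number of subjects, c the number who carry a course over and start nothing new, and n the number who start one on study. The row as written shows n/N and the overlap rule shows (c + n)/N, so the gap is c/N. N = 110 is the approximate maximum in SAP 3.3. The values of c and n are assumptions.

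- c = 6, n = 6: 6/110 = 5.5% as written; 12/110 = 10.9% by overlap; gap 6/110 = 5.5 points.
- c = 33, n = 11: 11/110 = 10.0% as written; 44/110 = 40.0% by overlap; gap 33/110 = 30.0 points.

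These figures restate the assumed c and n. They show how the gap behaves and do not estimate it.

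**The case against.** The strongest objection is that the effect depends on a record structure the documents do not show. Premedication is given around an infusion every 2 weeks, and the planned listing carries clock times at both ends, which suits dose-level records at least as well as long courses. If each administration is its own record, or courses are re-entered in ATB200-07, on-study use has a start date on or after Day 1 and is counted. This stands, and the point is conditional on it. Protocol 12.3.3 and the frequency column lean towards continuing records but do not settle the matter.

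A second objection is that the instruction in Protocol 13.1.3 to continue premedication concerns a subject who has an IAR under this protocol. Premedication begun after such an IAR starts after Day 1 and is counted. The passage does not show what was done in ATB200-03. This also stands: carry-over is plausible, but not documented.

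A third objection is that nothing is hidden. Carried-over drugs appear in the prior pre-infusion summary, the baseline characteristics (SAP 5.2.2), the concomitant table through limb (a), and the pre-infusion listing with dates. SAP 7.2.2.4 also lists, for each subject with an IAR, whether pre-infusion medication was given. This is correct, but none of these outputs gives the missing number. The prior row and the baseline item include drugs stopped before Day 1, the concomitant table does not label premedication, and the SAP 7.2.2.4 listing covers only subjects with an IAR. The pre-infusion listing would have to be counted by hand.

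A reader might infer that the report as a whole will understate on-study premedication, that subjects with a reaction history are left out, or that IAR rates are distorted. The documents do not support these readings. The possible shortfall is in one summary row, the subjects concerned remain in the adjacent prior row, and the IAR analyses in SAP 7.2.2 do not use this classification.

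**Conclusion.** The point holds for one descriptive summary. As written, SAP 5.2.4 classes a pre-infusion course begun before Day 1 and continued through ATB200-07 as prior only, contrary to limb (a) of its own concomitant definition. If premedication is recorded as continuing courses with original start dates, and if some subjects carried a course over, the on-study row is too low. For such records the rule can only undercount. The documents confirm neither condition and give no premedication rates, so no size can be stated. No endpoint changes and no hypothesis test is involved. What is lost is a reliable count of subjects premedicated during ATB200-07 to set beside the IAR tables.

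**What to change.** Align the pre-infusion definition in SAP 5.2.4 with limb (a). On-study should mean any pre-infusion medication taken from the first ATB200-07 dose up to and including the last dose, whatever its start date. In dates: start on or before the last dose date, and stop missing or on or after the first dose date. Say that a medication may count as both prior and on-study. State that first dose in the prior definition means the first ATB200-07 dose. Separate sub-rows for carried-over and newly started medication would help the reader but are optional.

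The cost is a sentence or two of SAP text and one changed derivation on dates the listing already requires. It needs no new data. The change concerns classification and reporting only, and does not touch how premedication is given.
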